Thermotape High-adhesion Medical Tape Comparison Study

June 21, 2022

Background:

Currently, modern medical tapes can be classified into two categories, high-adhesion tape, and low-adhesion tape. Both tapes, however, are not sufficient for use in a medical environment; high-adhesion tape, when removed, can cause medical adhesive related skin injuries (MARSI), which is liable to cause patients to have to return to the hospital to treat it, resulting in a dramatic increase in medical expenses once fully recovered. Conversely, low-adhesion tape is ill-suited for securing medical devices, such as IV lines, in place because of having low adhesion. As a result, a patient's ability to recover is impacted, overall increase medical expenses from an extended stay at the hospital.

Thermotape is designed to combat both flaws, by acting as a high-adhesion tape until heated, where it can be removed as easily as low-adhesion tape.

Objective:

This objective of this study is to compare the safety and performance of Thermotape compared to Tegaderm™ tape and Kind™ tape over the course of 24 hours. In regard to safety, pain inflicted during removal and any potential effects will be monitored for Thermotape versus Tegaderm™ and Kind™ tape.

Design:

A single blinded comparative clinical study, where researchers will know the tape being applied while the subjects do not.

Methods:

Consent will be obtained from the subject as they enter the building for tape application. This will be done by providing a paper consent form detailing the necessary details concerning the trial. If consent is obtained, they will be allowed into the room for tape application.

Before tape application, both forearms will be cleaned using an isopropyl alcohol wipe and skin markers will be used to draw lines, with two inches of spacing between, to separate areas of tape application. The marks began at the elbow and continued down the forearm. Following the pre-tape preparations process, Thermotape, Kind™ tape, and Tegaderm™ tape will be applied horizontally, in vertical

succession. Following Thermotape's application, a finger will be used to rub Thermotape in a vertical motion to ensure that the tape, especially edges, are fully adhered. The same procedure will be used for Kind™, however Tegaderm™ will not require the same adhesion procedure, as noted by a nurse practitioner. The tapes will be applied in a random order. Once all tapes are applied, researchers will give the following speech: "Now that the tapes have been applied, please do not do any physically extraneous activities, like swimming in the ocean, running a marathon, or storm chasing. Basically, any activities that make you sweat. Additionally, please do not shower until we remove the tapes, even if you really want to. If you do end up getting the tapes wet, through sweat or by showering, please note it down in the activity log on the back of your activity log. Also, try not to pick at the tapes, even if the corners start lifting. Thank you and we'll see you back tomorrow!" The speech requests that subjects are to not participate in strenuous physical activity or shower for the duration of the 24-hour study. One researcher is to apply the tape to the participants. Each tape will be cut 1 inch wide by 2 inches long.

When subjects return for tape removal, they will be given a pain survey, with a 0-to-10 Wong-Baker scale, to fill out after each piece of tape is removed. One photo will also be taken of the forearms to document the state of the subject's forearms 15 minutes after tape removal. Each piece of tape is then to be analyzed for wear using a 0-to-7 point scale.

When removing the tapes, an edge will first be lifted and then it will be peeled at an angle of 180° at a consistent rate. If a hair is encountered, the tape will be removed following the root of the hair to its tip. After the removal of each piece of tape, it will be placed on a glass slide and taped down for later quantification of cell and hair counting caused by tape removal. No gloves will be used throughout the process. During removal, if a subject shows signs of extreme discomfort or the skin appears to start tearing, manual removal will be stopped and a commercial silicon-based remover, Brava, will be used to remove the tape instead. To do so, Brava will be rubbed all over the tape, including the edges, and under the skin after removal of the tape. Gloves will be used in the case of using Brava to remove tape.

Removal of tape from both forearms will stay consistent, however one forearm (left), will use a Dynarex heat pack to assist in tape removal. Prior to heat pack activation, a corner for each tape sample will be lifted. After, the heat pack will be activated and kneaded for one minute before application onto the subject's skin. Then, the heat pack will be folded in half and applied to each piece of tape for 30 seconds before removal. The heat pack will be kneaded for 20 seconds between each tape removal.

Following the removal of all pieces of tape, the pain survey is collected, and each subject will be asked to wait 15 minutes following removal to examine for any redness that may have occurred. A 0-to-4 point scale will then be used to assess for erythema present on the forearms.

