## Primary Results:

### Pain experienced from Removal

The following 0-to-10-point Wong Baker scale will be used to quantify pain experienced by the subject during tape removal:

Subjects are to use the scale to determine the level of pain experienced after each piece of tape is removed and researchers are to record the number determined. Whole numbers between each face may be used as well.

The average for each population group will be obtained after data has been collected from the participants.

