### Skin Irritation

The following 0-to-4-point scale will be used to quantify the redness of the skin after tape removal:

Grade	Erythema/Irritation
0	None - natural skin tone
1	Slight - Barely visible increase in pink coloration
2	Mild - Visible increase in light pink coloration
3	Moderate - Diffuse pink coloration, localized or diffuse areas of reddened skin
4	Severe - Intense redness, diffused or localized

The average for each population group will be obtained after data has been collected from participants.

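### If the trial is meant to support the statement that heated Thermotape comes off as easily as low-adhesion tape, the supplied SAP text cannot do so: it plans pain averages only, with no within-subject difference, interval or margin.

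*Protocol*

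**What the plan says.** The protocol's Background states the design aim for the device: it should combine two properties "by acting as a high-adhesion tape until heated, where it can be removed as easily as low-adhesion tape". The second half of that sentence is a no-worse-than statement about heated Thermotape against low-adhesion tape.

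The protocol's Objective is broader. It is to "compare the safety and performance of Thermotape compared to Tegaderm™ tape and Kind™ tape over the course of 24 hours", and on safety "pain inflicted during removal and any potential effects will be monitored for Thermotape versus Tegaderm™ and Kind™ tape". It states no superiority, non-inferiority or equivalence hypothesis, and it labels neither comparator as the low-adhesion one.

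The protocol's Methods put all three tapes on each subject's forearms ("The tapes will be applied in a random order"). On the left forearm a heat pack is applied to every piece before removal; the right forearm has no heat pack.

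The SAP lists pain under Primary Results: "The following 0-to-10-point Wong Baker scale will be used to quantify pain experienced by the subject during tape removal". It adds "Whole numbers between each face may be used as well", so scores are integers. The planned analysis is one sentence: "The average for each population group will be obtained after data has been collected from the participants". The other primary result, Skin Irritation, has the same form: "The average for each population group will be obtained after data has been collected from participants".

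One part of the SAP and one figure were not available, so absence is judged on the supplied text. The SAP section on pain is among the supplied text.

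**The concern.** The Background sentence is the only place where either document says what heated removal should achieve, and pain on removal is the primary result that bears on it most directly. A reader of the final report will naturally hold the pain averages against that sentence.

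Averages alone cannot support or refute it. Two close averages may reflect equal tapes, or a real excess hidden by noise, and the plan has nothing that separates the two. Adding an ordinary difference test would not help: the smaller the study, the more often such a test is non-significant, so weak data would look like support. An interval without a margin shows the uncertainty but not how large an excess still counts as equal ease.

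The contrast is open as well. The low-adhesion reference is unnamed, and because every left-arm tape is heated, the reference could be its heated piece on the same arm or its unheated piece on the other. Those are different questions, and at present the choice could be made after the data are seen.

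**Working it through.** **Inputs from the documents.** Pain scale 0 to 10 in whole numbers; all three tapes on each subject, so differences can be taken within subject; heat on the left forearm only. The supplied text gives no sample size, SD, alpha, power or margin, so there is no plan figure to reproduce.

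**Assumptions, for illustration only.** SD of within-subject pain differences (heated Thermotape minus reference) of 1.5, 2 or 2.5 points; n = 10, 20, 30 or 40; a margin of 1 point as an example.

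**Step 1: what identical averages leave open.** The 95% interval for a mean paired difference has half-width t(0.975, n−1) × SD/√n. With SD 2:
- n = 10: 2.262 × 2/√10 = 1.43 points
- n = 20: 2.093 × 2/√20 = 0.94 points
- n = 40: 2.023 × 2/√40 = 0.64 points

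So even when the two averages agree exactly, a true excess of up to that size remains compatible with the data. This needs no significance test and applies directly to the averages that the SAP plans.

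**Step 2: what a non-significant test would be worth.** The supplied text specifies no test. If one were added later and non-significance read as similarity, the chance of missing a true 1-point excess is P(|T| < t(0.975, n−1)), where T is noncentral t with n−1 degrees of freedom and noncentrality √n × 1/SD. For SD 2 and n = 20 the noncentrality is √20/2 = 2.236 and the critical value 2.093, which gives 0.44.

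| SD | n = 10 | n = 20 | n = 30 | n = 40 |
|---|---|---|---|---|
| 1.5 | 0.53 | 0.19 | 0.06 | 0.02 |
| 2 | 0.71 | 0.44 | 0.25 | 0.13 |
| 2.5 | 0.79 | 0.60 | 0.44 | 0.31 |

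A normal approximation gives somewhat lower values (0.65 and 0.39 for SD 2 at n = 10 and 20). The t-based figures are the right ones for small paired samples.

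**Step 3: what a margin rule does.** The rule claims equal ease only if the upper 95% limit is below the margin. If the true excess equals the margin, the false-claim rate is 2.5% at every n, by construction (normally distributed differences assumed). If the tapes are truly equal, the chance of reaching the claim with a 1-point margin is P(T > t(0.975, n−1)), with noncentrality √n × 1/SD:

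| SD | n = 10 | n = 20 | n = 30 | n = 40 |
|---|---|---|---|---|
| 1.5 | 0.47 | 0.81 | 0.94 | 0.98 |
| 2 | 0.29 | 0.56 | 0.75 | 0.87 |
| 2.5 | 0.20 | 0.40 | 0.56 | 0.69 |

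**Step 4: sample size for that rule.** By the normal approximation, n = (SD × (1.96 + 0.842)/margin)² for 80% power. With a 1-point margin this gives 18, 32 and 50 subjects for SD 1.5, 2 and 2.5. The exact t calculation needs slightly more: at SD 2 it gives 0.75 for n = 30.

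**The case against.** The strongest reply is that the trial never undertakes to show similarity. The equal-ease sentence is Background and describes design intent. The Objective is a general comparison in which pain is monitored, and no supplied text says that equivalence or non-inferiority will be concluded. The same Background says that high-adhesion tape injures skin on removal, so a superiority question against a high-adhesion comparator fits the documents equally well. This stands, and it makes the point conditional.

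A reader might infer that equal ease is the hypothesis under test, and that the SAP would declare a tape that hurts a full point more to be equally gentle. The documents do not support this. The SAP contains no such decision rule; the supplied text obtains averages and does not specify a comparison of them.

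Two further objections also stand. The non-significance rates describe a test that the supplied text does not contain, with n and SD assumed, so they illustrate a general hazard and do not measure a defect of this plan. And 1 point is not a document value: it is the smallest step that one subject can record, which does not show what mean difference is acceptable.

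What survives is narrower. Every subject provides paired scores and pain is a primary result, yet the supplied plan makes no use of the pairing and gives no way to judge the one statement about heated removal that the protocol makes.

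**Conclusion.** The point holds in conditional form. If the trial is to support the equal-ease statement, the supplied SAP text is insufficient. The first gap is the missing within-subject contrast and interval, with the reference tape and its heat condition unnamed; the missing margin follows from that. If the sponsor does not intend such a conclusion, the paired difference and interval are still worth having, and the equal-ease wording should stay out of the conclusions.

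The size of the risk can only be given as a range. At SD 2, identical averages leave an excess of 0.64 points (n = 40) to 1.43 points (n = 10) compatible with the data. These figures rest on an assumed SD and n and on roughly normal paired differences. The judgement that the contrast, interval and margin are absent rests on the supplied text. It is a worthwhile and inexpensive improvement; it does not show that the trial will reach a wrong conclusion.

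**What to change.** In the SAP section on pain from removal:

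1. Name which comparator is the low-adhesion reference.
2. Name in advance the heat condition of that reference: its heated piece on the same left forearm, or its unheated piece on the right forearm. State that these answer different questions and which one is meant.
3. Report the mean within-subject pain difference, heated Thermotape minus that reference, with a 95% confidence interval, alongside the averages.
4. Conclude equal ease of removal only if the upper limit is below a margin that the sponsor fixes and justifies before data are seen. One point may serve as an example but needs its own justification. Otherwise report the difference and interval and state 'similarity not shown'.

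**Cost.** The analysis uses scores already being collected, so the change is to SAP wording, with no added visit or measurement. The real cost is that a small study may fail to reach the claim even when the tapes are equal. At n = 20 with a 1-point margin the chance of reaching it is 0.81, 0.56 or 0.40 for SD 1.5, 2 or 2.5. If the sponsor wants a good chance of making the claim, the sample size should be checked against the chosen margin, and that could mean more subjects.

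### Thermotape and Kind are finger-rubbed after placement and Tegaderm is not, so the Thermotape–Tegaderm contrast cannot separate the tape from the way it was applied.

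*Protocol*

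**What the plan says.** The Protocol (Objective) sets out to "compare the safety and performance of Thermotape compared to Tegaderm™ tape and Kind™ tape over the course of 24 hours". Under Methods, once Thermotape has been placed, "a finger will be used to rub Thermotape in a vertical motion to ensure that the tape, especially edges, are fully adhered". For the second tape, "The same procedure will be used for Kind™". The third is exempted: Tegaderm "will not require the same adhesion procedure, as noted by a nurse practitioner".

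Two other features of application are described: "The tapes will be applied in a random order", and "One researcher is to apply the tape to the participants". The Protocol gives no force, duration or number of strokes for the rub. It does not say how Tegaderm is pressed on, and it cites no product instruction for leaving the step out.

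The SAP sections on pain, skin irritation, skin cells, tape wear, hair follicles and TEWL each describe averages, by group or by brand. None of them mentions the application step.

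**The concern.** By the Protocol's own account the rub is there to secure adhesion, and adhesion is the property under test. The Background presents Thermotape as a tape that holds firmly until heated and then comes off easily. How well a strip is stuck down at the start can plausibly affect how well it holds over 24 hours and how much it pulls on skin and hair when peeled.

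A step that acts on adhesion is given to the new tape and one comparator and withheld from the other comparator. Tegaderm is one of only two comparators named in the Objective. If the Thermotape and Tegaderm averages differ, the reader will want to attribute the difference to the tapes, and the design does not allow that.

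**Working it through.** The plan has no figure to reproduce. The check is whether the design can separate the rub from brand.

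**Inputs (Protocol, Methods).** Thermotape is rubbed, Kind is rubbed, and Tegaderm is exempt. Order is random, and one researcher applies the tapes.

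**Coding.** Let K = 1 for Kind, T = 1 for Tegaderm and R = 1 if the strip is rubbed.

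| Tape | Intercept | K | T | R |
|---|---|---|---|---|
| Thermotape | 1 | 0 | 0 | 1 |
| Kind | 1 | 1 | 0 | 1 |
| Tegaderm | 1 | 0 | 1 | 0 |

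For every strip R = 1 − T. The model has 4 columns but rank 3, so the Tegaderm effect and the rub effect are not separately estimable.

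**Contrasts.** Write the mean outcome as μ + κK + τT + ρR, where κ and τ are the Kind and Tegaderm effects relative to Thermotape and ρ is the effect of rubbing.

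- Thermotape mean: μ + ρ
- Kind mean: μ + κ + ρ
- Tegaderm mean: μ + τ
- Thermotape − Tegaderm = (μ + ρ) − (μ + τ) = −τ + ρ. The whole rub effect is carried into the difference.
- Thermotape − Kind = (μ + ρ) − (μ + κ + ρ) = −κ. The rub cancels.
- Heated − unheated within one brand: the Protocol makes no difference in application between the forearms, so R is the same on both and cancels.

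**What does not help.** Random order balances position on the forearm, within-subject comparison removes differences between people, and a single applicator makes the rub more consistent. None of these changes R = 1 − T. More subjects only estimate −τ + ρ more precisely. Covariate adjustment fails because of the rank deficiency, whatever the analysis method.

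**Direction.** Assume rubbing raises adhesion, so that ρ pushes removal force and holding upwards.

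- Pain (0–10) and redness (0–4): higher is worse, so ρ > 0 moves the difference against Thermotape. Cell and hair counts would follow the same logic.
- Wear (0–7): higher is better, so ρ > 0 moves the difference in favour of Thermotape. The link is most direct here. The rub is aimed particularly at edges, and grades 5 to 7 are separated by lifted edges and adhered corners.
- TEWL: the mixing is the same, but I claim no direction.

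**Size.** ρ cannot be estimated from this design, and the documents give no figure for it.

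**The case against.** The strongest reply is that this is a choice of what to compare. The purpose of the rub is full adhesion. If Tegaderm reaches that state without it, each tape has been brought to the same condition by the handling it needs, and the contrast is of each product as used. On that view a uniform rub would replace one legitimate comparison with another.

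Part of this stands. An as-used comparison is defensible, and ρ may be close to zero. But the Protocol does not say that this is the comparison intended. Its only support is a practitioner's remark that the step is not needed, and it specifies no application procedure for Tegaderm. If the remark is right, rubbing Tegaderm as well changes little. If it is wrong, the uniform rub removes a bias.

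It is also fair to say that lower contact pressure on Tegaderm is not documented. What is documented is a different procedure, and the point needs no more than that.

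Three stronger readings are tempting, and the documents do not support them:

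- **That the different handling breaks the blind.** The Design says that "researchers will know the tape being applied while the subjects do not". Thermotape and Kind are handled alike, so the rub cannot tell a subject which strip is Thermotape. At most it marks one strip as different, and nothing says subjects are told which brand is treated differently.
- **That the imbalance favours the new tape.** On pain and redness, the two outcomes listed as primary, the likely direction is the opposite. A Thermotape advantage there would, if anything, be understated.
- **That a false-positive rate can be attached.** That would need a rub effect, a standard deviation, a sample size and a stated test. The text available here supplies none of these, so any such figure would be pure assumption.

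**Conclusion.** The point holds for one of the two comparator contrasts. As written, the Thermotape–Tegaderm difference on all six outcomes estimates brand plus rubbing, and no analysis can divide it. Thermotape–Kind and the within-brand heated–unheated contrasts are untouched by this issue.

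The failure to separate the two effects follows from the application rule alone and needs no numerical assumption. The size is unknown. The direction depends on the assumption that rubbing raises adhesion, which is the purpose the Protocol gives for it. On that assumption the effects run in opposite directions: worse pain and redness for Thermotape, better wear. A result of firmer hold with more pain relative to Tegaderm could then arise partly or wholly from handling. This does not invalidate the study. It is an avoidable ambiguity in a named comparison and is cheap to remove.

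**What to change.** In the Protocol's Methods, replace the Tegaderm exception with one rule for all three tapes: after placement, every strip gets the same finger rub, in the same motion, for the same stated number of strokes, by the same researcher. With R = 1 for every strip, the rub no longer differs between the tapes being compared.

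The cost is one sentence and a few seconds per strip. The small downside is that Tegaderm receives a step its usual application may not need.

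If there is a product reason not to rub Tegaderm, state it with its source, write out the procedure for each tape, and limit the Thermotape–Tegaderm conclusion to the tape plus its application procedure. If strips have already been applied under the present rule, only that limitation is available, and it should appear wherever the contrast is reported.

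### The order of forearms and strips at removal is neither specified nor balanced, so serial pain scores can bias the heated-versus-unheated contrast and, under a habitual peel order, the brand contrast

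*Protocol*

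**What the plan says.** Protocol, Methods, describes the layout as "Thermotape, Kind™ tape, and Tegaderm™ tape will be applied horizontally, in vertical" succession down the forearm, and then states: "The tapes will be applied in a random order". It does not say how the order is drawn, whether it means position on the arm or sequence in time, or whether a subject's two arms share it.

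For removal, the same section says "Removal of tape from both forearms will stay consistent", except that "one forearm (left), will use a Dynarex heat pack to assist in tape removal". The heating sequence is given in detail. First, "the heat pack will be activated and kneaded for one minute before application onto the subject's skin". After that, "the heat pack will be folded in half and applied to each piece of tape for 30 seconds before removal", with 20 seconds of further kneading between strips. The removal text also covers edge lifting, peel angle, peel rate and hair direction. It gives no rule for which forearm is done first or which strip is peeled first.

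Pain is rated serially. The Protocol provides a survey "to fill out after each piece of tape is removed", and the SAP (Primary Results, Pain experienced from Removal) repeats this: "Subjects are to use the scale to determine the level of pain experienced after each piece of tape is removed". The SAP plans an average for each group, with no term for order, position or arm. Under Design, the Protocol states that the researchers are not blinded to the tape.

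**The concern.** Each subject gives several pain scores within one short session. Such scores can change along the sequence for reasons unrelated to tape or heat: a subject may anchor on the first peel, become more sensitive, or become used to it. Randomising where the tapes go within an arm gives no protection against a constant order of arms. A site could follow the text exactly and always do the heated left arm last, or always first. Every heated score would then come from one half of the sequence and every unheated score from the other.

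Within an arm, the order of peeling is left to people who know the brands. If they peel in a habitual brand order, the random placement is lost at the point where pain is measured. On the left arm, brand would then also go with how long the pack had been active.

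Pain at removal is listed under Primary Results. If removal position is not recorded, no later analysis can correct for it.

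**Working it through.** The available text gives no sample size, power, alpha or expected difference, so there is no figure of the plan to reproduce. The calculation below shows how large an order effect could be.

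**Inputs from the documents**
- Three tapes on each of two forearms: 3 × 2 = 6 strips per subject. The number six is inferred, not printed.
- Pain is scored from 0 to 10 after each strip.
- Heat is used on the left forearm only.
- One pack (inferred from the wording) is kneaded for 60 s, applied for 30 s per strip, and kneaded for 20 s between strips.

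**Assumptions, not in the documents**
- d: additive linear drift per successive peel, 0.1 to 0.3 points, direction unknown.
- r: time to peel and score one strip, 5 to 60 s.

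**Heat contrast, one arm always first**
- Mean position of the first arm: (1 + 2 + 3)/3 = 2. Mean position of the second: (4 + 5 + 6)/3 = 5.
- Bias = (5 − 2) × d = 3d in size, which is 3 × 0.1 = 0.3 to 3 × 0.3 = 0.9 points.
- Strip order within an arm does not matter, because each arm uses the same three positions in any order. Every subject carries the same shift, so averaging over more subjects leaves it unchanged.

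**Brand contrast within an arm**
- Habitual brand order: d between adjacent brands (0.1 to 0.3 points) and 2d between first and last (0.2 to 0.6 points).
- Peeling by randomised position: expected bias 0. Two of three positions drawn at random differ by ±1 with probability 4/6 and by ±2 with probability 2/6. The variance is 4/6 + 8/6 = 2, so the per-subject SD is 1.41d.

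**Heated strip of one brand against unheated strip of another, unheated arm always first**
- With the same habitual order on both arms, the gap in positions is 3 + i − j, where i and j are the brands' places within an arm. For i ≠ j this is 1, 2, 4 or 5.
- The gap is 3 only on average over balanced tape orders.

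**Time since pack activation when heating starts (left arm)**
- Strip 1: 60 s.
- Strip 2: 60 + 30 + r + 20 = 110 + r, which is 115 to 170 s.
- Strip 3: 110 + r + 30 + r + 20 = 160 + 2r, which is 170 to 280 s.

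These are elapsed times. The documents show no temperature change over them.

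**After balancing arm order**
- Half the subjects contribute +3d and half −3d to the heat contrast, so the mean bias is 0. This cancellation holds for any additive position pattern, not only a linear one. Carry-over that itself depends on whether the heated arm came first need not cancel.
- What remains is between-subject noise with SD 3d (0.3 to 0.9 points per subject). Adjusting for position takes out the part that follows the modelled drift.

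**The case against.** The strongest reply is that the evidence is silence. Nothing says arms or brands are removed in a fixed order, and one part of the SAP and a figure were not available in the text reviewed. That the pack is used on the left arm fixes which arm is heated, not when it is done. This stands: the defect is an unspecified order, and the bias is conditional on what sites do.

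The brand comparison may already be protected. If strips come off down the arm, and the random order means random position, brand is balanced in expectation against both peel position and time since activation. This also stands, so the brand part is stated as conditional. The text does not require that order of peeling.

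A reader might infer that pack drift confounds heated with unheated removal. It does not. The right arm has no pack, so any change in the pack is part of the heat treatment. Nor is a change shown: the repeated kneading may keep the pack consistent.

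The heat contrast is not named as a formal comparison, and it is already aliased with the left forearm. Both are true. However, heat-triggered release is the product's purpose in the Background, and heating one arm only invites the comparison. A second source of bias is not excused by the first.

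Finally, drift size and direction are assumed, and anchoring on a first peel would not be linear. This limits the figures to illustration.

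**Conclusion.** The concern holds in conditional form. A plan followed to the letter permits one forearm always to be removed first. In that case the heated-versus-unheated pain contrast is biased by 3d: 0.3 to 0.9 points for an assumed linear drift of 0.1 to 0.3 per peel, sign unknown. Neither a larger sample nor random placement within the arm removes this.

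The brand contrast is at risk only under a habitual brand order at removal. The bias is then d to 2d, and brand on the left arm is also aliased with pack time: 60 s for the first strip against 160 + 2r s for the third.

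Three stronger readings are not supported. The documents do not say that removal order is fixed. They do not show that the pack cools or that brand comparisons are biased as planned. And heated Thermotape against an unheated comparator does not always differ by three positions: under a habitual brand order with one arm always first, the gap is 1, 2, 4 or 5.

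The conclusion rests on six serial strips and one pack per subject (both inferred) and on the assumed d and r. It concerns pain scores only; erythema is graded after all removals.

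**What to change.** - For each subject, allocate at random, in equal numbers, which forearm is removed first.
- State that the random tape order is the order of positions on the arm. Peel strictly from elbow to wrist on both arms, so that the randomised position also fixes the removal order.
- Use the six possible tape orders in equal numbers, and state whether a subject's two arms share one order. If they do, the list has 6 × 2 = 12 sequences.
- Record removal position (1 to 6) with each pain score, and report the pain contrasts adjusted for position.

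The cost is a prepared sequence list, one extra column on the pain form and slightly more analysis. No visits or procedures are added.

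This does not remove the separate aliasing of heat with the left forearm. That would require the heated side itself to be randomised, and randomising the side alone would not cure the order problem.
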